### 12.3. Dose Interruption

Dose interruptions will be recorded in the subject's diary and eCRF. All dose interruptions reported are protocol-allowed interruptions due to safety reasons. Number and percent of subjects who interrupted study drug(s) will be presented.

Basic summaries of length of interruption (days) will be presented for each interruption. Dose interruption due to COVID-19 will be summarized and listed.

### 12.4. Adverse Events

The adverse event verbatim descriptions (Investigator terms from the eCRF) will be classified into standardized medical terminology using MedDRA. Adverse events will be coded to primary SOC and PT using MedDRA.

Adverse events that occur between the time subject signs the ICF for the study and the time when subject receives his/her first dose of study drugs on Day 1 will be summarized as medical history and not as a TEAE unless the event meets the definition of an SAE.

TEAEs are those AEs that occurred on or after the date of first dose of study drugs and within 28 days after the last dose of ALIS/ELC, AZI, or ETH, whichever study drug is stopped last. The listing will indicate whether a non-TEAE occurred post-treatment with study drugs.

The following table describes rules to be applied in case of missing AE start date.

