3.4. End of Treatment

The EOT is defined as the date when the EOT visit occurs. The EOT visit will occur when the subject returns for EOT visit after discontinuation or completion of ALIS/ELC treatment only. Discontinuation or completion of AZI and/or ETH does not constitute EOT.

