4.2. Discontinuation of Study Drugs and Participant Discontinuation/Withdrawal

4.2.1. Discontinuation of Study Drugs

All subjects are encouraged to stay in the study for continued safety monitoring regardless of discontinuation of study drugs. If a subject discontinues one or more study drugs (ALIS/ELC, AZI, and/or ETH), they will remain on the other study drug(s) and continue with the scheduled study visits. For these subjects, it is highly encouraged to stop all MAC treatment at Month 6 (per study design) to evaluate the primary and secondary endpoints during the off treatment period. However, if deemed medically necessary per the Investigator, these subjects who prematurely discontinue one or more study drugs may be allowed to continue treatment during the off treatment period.

If a subject discontinues ALIS or ELC:

- The reason for ALIS or ELC discontinuation will be recorded in eCRF.
- The subject will remain on the other study drugs (AZI and ETH) and continue with the next scheduled study visit.
- At the next scheduled visit, the subject will complete the EOT visit assessments.
- The subject will complete a Month 6 visit when they reach Month 6.

If a subject discontinues AZI and/or ETH, the reason for drug discontinuation should be recorded in the eCRF. The EOT visit should not be completed at this time. The subject will remain on the other study drugs (ALIS/ELC and AZI or ETH) and should initiate therapy consistent with the 2020 ATS/ERS/ESCMID/IDSA treatment guidelines ([Daley et al., 2020](#)), and continue with the next scheduled study visit. Any changes to therapy and treatment regimen should aim to prevent the development of macrolide resistance. Changes to treatment should be discussed with the Medical Monitor to ensure compliance with the 2020 ATS/ERS/ESCMID/IDSA treatment guidelines.

For subjects who discontinue one or more study drugs, replacement therapy may be provided at the discretion of the Investigator; this is not considered rescue therapy.

Subjects may be discontinued from one or more study drugs at the discretion of the Investigator if they meet treatment stopping criteria per local labeling guidance.

If a subject withdraws consent from continued safety monitoring, the EOS visit should be completed.

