9.9.1. Definition of an Adverse Event

An AE is defined as any untoward medical occurrence in a subject or clinical investigation subject administered a pharmaceutical product and which does not necessarily have to have a causal relationship with this treatment. An AE can therefore be any unfavorable and unintended sign (including an abnormal laboratory finding, for example), symptom, or disease temporally associated with the use of a medicinal product, whether or not considered related to the medicinal product.

Medical occurrences that begin after obtaining informed consent, but before administration of study drugs will be recorded under medical history/Current Medical conditions, not as AEs.

Treatment-emergent adverse events are AEs that occurred on or after the date of first dose of study drugs and within 28 days after the end of treatment.

It is the responsibility of Investigators, based on their knowledge and experience, to determine, those circumstances or abnormal laboratory findings which should be considered adverse events.

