10.7.3. Adverse Event Analyses

Adverse events will be coded using MedDRA by system organ class and preferred term. The severity of AEs will be graded to either mild, moderate, or severe.

The number and percent of subjects with AEs will be presented by treatment group. The severity of AEs, the relationship to study drugs (ALIS/ELC, AZI, ETH), AEs leading to study discontinuation, TEAEs, AESIs, and SAEs will be similarly presented. Treatment-emergent and treatment-related AEs will be tabulated by system organ class and preferred term.

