#### 3.2. Secondary Objectives and Endpoints

To evaluate the effect of each treatment arm (ALIS + background regimen and ELC + background regimen) on the following:

Objective	Endpoint
Culture conversion by Month 6	Proportion of subjects achieving culture conversion by Month 6 (negative cultures for MAC at Month 5 and Month 6)
Patient-reported respiratory symptoms at Month 7	Change from Baseline to Month 7 in respiratory symptom score
Patient-reported fatigue symptoms at Month 7	Change from Baseline to Month 7 in fatigue symptom score

Objective	Endpoint
Time to culture conversion	Time to culture conversion (first of 2 consecutive negative cultures) of Baseline to EOT assessments
Time to first negative culture	Time to first negative culture of Baseline to EOT assessments
MAC isolates with amikacin MIC $\geq 128$ $\mu\text{g}/\text{mL}$	Proportion of subjects who develop a MAC isolate with amikacin MIC $\geq 128$ $\mu\text{g}/\text{mL}$ at more than 1 visit at any timepoint during the study
Recurrence of MAC (relapse)	Proportion of subjects who achieved culture conversion and subsequently have at least 1 MAC positive culture in agar media or positive cultures in broth media in at least 2 consecutive visits that is the same species and genome as cultured at Screening/Baseline.
Recurrence of MAC (new infection)	Proportion of subjects who achieved culture conversion and subsequently have at least 1 MAC positive culture in agar media or positive cultures in broth media in at least 2 consecutive visits that is different than cultured at Screening/Baseline (different species or same species but different genome).
Safety and tolerability of ALIS + background regimen	Incidence and severity of AEs and TEAEs and other safety variables (eg, vital signs, physical examination, clinical laboratory values) from Baseline through the EOS

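### SAP 12.4 and 12.5 tabulate only treatment-emergent events by arm, so late AEs in subjects who stop all three drugs early but stay in follow-up are left to listings, although the safety endpoint runs through EOS

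*SAP*

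**What the plan says.** **Endpoint.** Protocol 2.2 and SAP 3.2 define it as "Incidence and severity of AEs and TEAEs and other safety variables", with Baseline through EOS as the period. AEs and TEAEs are named separately.

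**Protocol analysis plan (10.7.3).** "The number and percent of subjects with AEs will be presented by treatment group". Severity and relationship follow, and "AEs leading to study discontinuation, TEAEs, AESIs, and SAEs will be similarly presented". For coded tables the scope is narrower: "Treatment-emergent and treatment-related AEs will be tabulated by system organ class and preferred term". The synopsis (Statistical Analyses) also plans summaries of all AEs and of SAEs.

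**TEAE window.** Protocol 9.9.1 closes it "within 28 days after the end of treatment", where EOT follows ALIS/ELC alone: "Discontinuation or completion of AZI and/or ETH does not constitute EOT" (Protocol 3.4). SAP 12.4 closes it "within 28 days after the last dose of ALIS/ELC, AZI, or ETH, whichever study drug is stopped last".

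**SAP outputs.** Every row of the SAP 12.4 overview (any, serious, severe, fatal, related, special interest, leading to withdrawal, COVID-19) is a TEAE count. So are the SOC/PT and maximum-severity tables. SAP 12.5 summarizes TEAESIs. Later events are marked as post-treatment in the AE listing, and SAP 12.6 lists fatal AEs. Table 9 declares one change from the protocol, the EOT definition.

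**Follow-up after stopping.** Under Protocol 5.2.2, rescued subjects stop the randomized regimen and keep attending visits. SAP 4.1 says safety data continue to be collected after discontinuation, up to 7 months from randomization.

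**The concern.** The endpoint and Protocol 10.7.3 call for two quantities: events under treatment, and all events on study. The SAP delivers only the first in tables. For most subjects the two coincide. They separate when a subject stops everything early and stays. The plan encourages exactly that, and it uses such subjects' later data for culture conversion and PROs. Laboratory values and vital signs are also summarized at all post-baseline visits, so AEs are the truncated part of the safety endpoint.

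What is at stake is completeness. A reader who wants the number of subjects per arm with an SAE, AESI, severe AE or fatal AE through EOS would have to add flagged events from a listing by hand. With about 50 subjects per arm, one such subject is 1/50 = 2 percentage points. Rescue is triggered by progression on randomized treatment, so the affected numbers could differ between arms.

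**Working it through.** **Inputs.** A month is 28 days (SAP 7.6.1). The TEAE window is 28 days after the last dose (SAP 12.4). Follow-up runs to Month 7 (SAP 4.1), and visit windows are ±7 days (Protocol Table 4). There are 50 subjects per arm (SAP 4.3.1). Last dose is taken to mean the last dose of randomized study drug.

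**The SAP's own window.** The exposure-adjusted rate uses last dose + 29 − first dose as time at risk. For a first dose on Day 1 and last dose on Day 56, this is 56 + 29 − 1 = 84 days. Counting inclusively from Day 1 to Day 56 + 28 = Day 84 also gives 84. The two agree.

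**Who is affected.**

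- Completers: no planned gap, since 196 − 168 − 28 = 0. At the extremes of both visit windows it is (196 + 7) − (168 − 7) − 28 = 14 days.
- Subjects who leave the study: EOS is 28 days after the last dose (Protocol 4.2.3), so essentially no gap.
- Subjects who stop only ALIS/ELC: "The subject will remain on the other study drugs (AZI and ETH) and continue with the next scheduled study visit" (Protocol 4.2.1). With the EOT visit at Month 4 and AZI/ETH to Month 6, the protocol window leaves 196 − 112 − 28 = 56 days uncovered. The SAP window leaves 196 − 168 − 28 = 0.
- Subjects who stop all three drugs and stay: this is where the gap lies.

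**Size of the gap for one such subject.** Uncovered days = 7 × 28 − 28m − 28 = 168 − 28m, for last dose at Month m.

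| Last dose of all drugs | Uncovered days | Share of 196 days |
|---|---|---|
| Month 1 | 140 | 71% |
| Month 2 | 112 | 57% |
| Month 3 | 84 | 43% |
| Month 4 | 56 | 29% |
| Month 5 | 28 | 14% |
| Month 6 | 0 | 0% |

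**Size at arm level (assumed counts).** The documents give no rate of rescue or of stopping all drugs. If k of 50 stop everything at Month 3, the uncovered share of the arm's planned follow-up is 84k / (50 × 196) = 84k / 9800. That is 0.9%, 1.7% and 4.3% for k = 1, 2 and 5. A more extreme assumption, 10 of 50 stopping at Month 2, gives 10 × 112 / 9800 = 11.4%. These are shares of time, not of events.

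**Incompletely dated events.** SAP Table 7 has no upper limit. A late AE with the onset day missing is therefore classed as a TEAE and is counted. The gap concerns events with a complete onset date.

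**The case against.** The strongest case is that this is ordinary practice with little consequence, and much of it stands.

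- *The 28-day window is the protocol's own.* This stands. A reader might infer that the SAP cut-off is wrong or too short. The documents do not support that: Protocol 9.9.1 uses the same 28 days, and for subjects who stop only ALIS/ELC the SAP window is the wider one.
- *The SOC/PT tables are planned as treatment-emergent.* This stands. Protocol 10.7.3 says so, and those tables are not a departure.
- *The synopsis speaks of safety parameters between Baseline and EOT.* If that phrase governs AEs, the SAP covers more than the synopsis asks. But it directly follows the laboratory, vital-sign and examination changes and may apply only to them. The same section plans summaries of all AEs, and the phrase does not override an endpoint that runs to EOS.
- *Most counts would not move.* This largely stands for the any-AE row. A subject with an earlier TEAE is already counted, and Protocol 9.9.6 reports that in INS-212, a refractory population, most ALIS-treated subjects had their first AE within 60 days. It says less about SAEs, AESIs or severe events, which are rarer per subject.
- *Nothing is lost.* Every AE is listed and late ones are flagged, so a reader should not infer that late events are hidden. Nor do the documents show that a late death would be missing from every by-arm table: the overview has a fatal-TEAE row, and disposition (SAP 8.1) gives reasons for discontinuation, whose categories are not shown.
- *Differences will be explained in the CSR (SAP 2).* That covers disclosure but does not produce the count.

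**Conclusion.** The point holds as a minor mismatch between endpoint and tables. The endpoint and Protocol 10.7.3 call for by-arm counts of all AEs, SAEs and AESIs; SAP 12.4 and 12.5 plan only treatment-emergent ones, and Table 9 does not declare the restriction. It reaches only subjects who stop all three drugs early and stay in follow-up, chiefly those rescued, and only fully dated events more than 28 days after the last dose. For each such subject 28 to 140 days fall outside the AE tables, assuming a last dose between Month 5 and Month 1 and attendance to a nominal Month 7. The number of such subjects is unknown, probably small and possibly zero.

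Confidence is high on the text and the day arithmetic, and low on the practical effect. The documents do not support a claim that the arm comparison of safety is biased. The primary objective, PRO validation, is untouched.

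**What to change.** Add one descriptive overview by arm on the safety analysis set. It should count subjects with any AE, SAE, AESI, severe AE or fatal AE with onset from first dose through EOS, and give all on-study deaths by arm. Add a footnote that events after rescue occurred under unblinded local therapy, which may include ALIS in control subjects. Keep the TEAE tables as the main view, and leave the TEAE definition and the SOC/PT tables unchanged.

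The cost is one table and a footnote from data already collected. The downside is that late events mix post-rescue treatments, so the table serves completeness and cannot attribute events to ALIS. A row in Table 9 declaring the restriction would be honest documentation, but it would not by itself deliver the stated endpoint.

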**Table 7: TEAE Assignment in Case of Missing AE Start Date Elements**

Missing elements of AE start	Rule (study drug start = first dose of ALIS/ELC, AZI, or ETH, whichever is started first)	Classification
Regardless of any missing information for AE start: AE end date < study drug start date		non-TEAE
Otherwise (ie, if AE end date ≥ study drug start date)		
day/month/year	all AEs	TEAE
day and month	AE start year ≥ study drug start year	TEAE
	AE start year < study drug start year	non-TEAE
day	AE start month/year ≥ study drug start month/year	TEAE
	AE start month/year < study drug start month/year	non-TEAE

The exposure-adjusted incidence rate (EAR) is defined as the number of subjects with a particular AE divided by the total time at risk for TEAEs among subjects in the respective study treatment group at risk of an initial occurrence of the event.

$$\text{time at risk for TEAE (days)} = \text{minimum (date of last dose of study drug + 29, EOS date)} - \text{date of first dose of study drug,}$$

where 'study drug' may be ALIS/ELC, AZI, and/or ETH.

The EAR will be presented for tables summarizing TEAE.

Duration of AEs will be calculated in days (see [Section 7.6.1](#)). If date of onset or end date of event is not complete, duration will be set to missing.

Tabulations that are displayed by SOC and PT will be ordered by descending order of total incidence of SOC and PT within each SOC. Tabulations of the following types will be presented:

- Overall incidence of TEAEs including the incidence of subjects with at least one:
  - TEAE
  - serious TEAE

- severe TEAE
- TEAE resulting in death
- TEAE related to ALIS/ELC, related to AZI, related to ETH
- serious TEAE related to ALIS/ELC, related to AZI, related to ETH
- TEAESI
- TEAE leading to ALIS/ELC withdrawal, AZI withdrawal, ETH withdrawal
- TEAE related to COVID-19
- Subject incidence of TEAEs and total number of TEAEs by MedDRA SOC and PT:
  - TEAEs
  - TEAEs related to ALIS/ELC, related to AZI, related to ETH
  - serious TEAEs
  - serious TEAEs related to ALIS/ELC, related to AZI, related to ETH
  - TEAEs leading to ALIS/ELC withdrawal, AZI withdrawal, ETH withdrawal
  - TEAEs, PT with incidence of >5% in any treatment group
- Subject incidence of TEAEs by MedDRA SOC, PT, maximum severity. At each level of subject summarization, a subject will be classified at the highest reported severity. Missing severity will be classified as missing on the summary if there is no non-missing severity at the level of summarization.

All information pertaining to AEs noted during the study will be presented in a subject listing.

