4.2.3. Early Discontinuation Procedures

If a subject prematurely discontinues the study, the subject will do the following:

- Attend the EOT visit
- Attend EOS visit 28 days after the last dose of study drugs
- Complete EOS assessment

If a subject withdraws from the study, the Investigator will complete and report the observations as thoroughly as possible up to the date of withdrawal including the date of last treatment and the reason for withdrawal.

If the subject is discontinued from the study due to an AE, the Investigator will follow the subject until the Investigator deems that the AE has resolved or stabilized. In case of unresolved AEs including significant abnormal laboratory values at the EOS assessment, these events will be followed up until resolution or until they become stable.

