9.9.6. Management of Adverse Events

Initial education of adverse effect expectations is crucial for subjects initiating study drugs in order to maintain retention of subjects in the study. Based on data from the ALIS development program, there is an association with ALIS and respiratory symptoms (eg, cough, dyspnea) reported as AEs, likely from airway irritation by the inhaled antibiotic. Data observed from Study INS-212 (refractory MAC population) show that the majority of subjects treated with ALIS experienced their first AE within 60 days of initiating ALIS. Azithromycin may cause gastrointestinal symptoms. Subjects should be monitored for visual acuity when taking ethambutol.

Data have shown that specific interventions may be helpful in the management of TEAEs ([Swenson et al., 2020](#)). Pretreatment with a bronchodilator, move administration of ALIS to the evening, antitussives, post-dose gargle (warm liquid or glycerin), and other interventions may help with management of TEAEs.

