### **7.4.4. Missing Start and Stop Dates for Adverse Events**

The rules to categorize AEs to 'TEAE' or 'non-TEAE' are described in [Section 12.4](#). There is no need to impute missing or partially missing start or stop dates.

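### SAP 12.4 words the exposure-adjusted incidence rate as a first-event rate, but its time-at-risk formula has no onset date and keeps counting time after the first event

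*SAP*

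**What the plan says.** The sentence in SAP 12.4 below Table 7 divides a subject-level count (each subject with the AE counts once) by the total "time at risk for TEAEs among subjects in the respective study treatment group at risk of an initial occurrence of the event". The formula that follows ends each subject's time at "minimum (date of last dose of study drug + 29, EOS date") and subtracts the date of first dose. A note adds that the study drug in this formula may be ALIS/ELC, AZI and/or ETH. On scope, SAP 12.4 states: "The EAR will be presented for tables summarizing TEAE".

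Three other provisions bear on the point:

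- The TEAE definition in SAP 12.4 runs from first dose to "within 28 days after the last dose of ALIS/ELC, AZI, or ETH, whichever study drug is stopped last".
- Table 7, titled "TEAE Assignment in Case of Missing AE Start Date Elements", counts some events with incomplete onset dates as TEAEs, while SAP 7.4.4 says "There is no need to impute missing or partially missing start or stop dates".
- Protocol 10.7.3 plans numbers and percentages of subjects with AEs. It does not mention an exposure-adjusted rate.

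**The concern.** A subject is at risk of an initial occurrence only until the event occurs. The formula gives each subject the same number of days for every AE row, whether or not and whenever the event happened. No other section of the protocol or SAP stops time at the first event. A programmer who follows the sentence and one who follows the formula would therefore produce different tables from the same data.

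What is at stake is the meaning of the rate column in the TEAE tables. Events that are common and early are affected most. The protocol itself expects early onset: section 9.9.6 reports from the refractory-population study that "the majority of subjects treated with ALIS experienced their first AE within 60 days of initiating ALIS".

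**Working it through.** The plan gives no EAR value, so there is no figure to reproduce. It also gives no scaling unit; rates here are per 100 patient-years.

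**Inputs from the documents.** Treatment lasts 6 months (SAP 4.2) and a month is 28 days (SAP 7.6.1), so the last dose falls on day 168. The TEAE window adds 28 days, so T = 168 + 28 = 196 days.

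**Assumed inputs.** Incidence p and onset day t are not in the documents and are shown as ranges. The main calculation also assumes the full window T for every subject.

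**The formula for a completer.** With first dose on day 1 and last dose on day 168, it gives min(197, EOS day) − 1. That is 196 days if EOS is day 197 or later, and 195 if EOS is day 196. The last-dose branch counts days inclusively and the EOS branch does not. The EOS branch applies, for example, when a subject who leaves early follows Protocol 4.2.3: "Attend EOS visit 28 days after the last dose of study drugs".

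**Two rates.**

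- SAP formula: p / 196 × 36525
- Time stopped at first onset: p / [p × t + (1 − p) × 196] × 36525
- Shortfall of the first against the second: p × (1 − t/196)

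At p = 50% and t = 45, the formula gives 0.5/196 × 36525 = 93.2. Stopping at onset gives 0.5/(22.5 + 98) × 36525 = 151.6. The shortfall is 0.5 × (1 − 45/196) = 38.5%.

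| Incidence p | SAP formula | First-event rate, onset day 45 | Shortfall, day 45 | Shortfall, day 90 to day 15 |
|---|---|---|---|---|
| 50% | 93.2 | 151.6 | 38.5% | 27% to 46% |
| 20% | 37.3 | 44.1 | 15% | 11% to 18% |
| 5% | 9.3 | 9.7 | 3.9% | 2.7% to 4.6% |

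Under a constant hazard no onset day is needed. The first-event rate is −ln(1 − p)/196 × 36525 = 129.2, 41.6 and 9.6, and the shortfalls are 28%, 10% and 2.5%.

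**Effect of early stopping.** Take 50 subjects in an arm (SAP 4.3.1), 25 of them with a first event at day 60. First-event time is 25 × 60 + 25 × 196 = 6400 days.

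- All subjects have full windows: formula time is 50 × 196 = 9800 days; shortfall 1 − 6400/9800 = 35%.
- 10 of the 25 stop all drugs at day 60, so their window is 60 + 28 = 88 days: 10 × 88 + 40 × 196 = 8720 days; shortfall 1 − 6400/8720 = 27%.
- All 25 stop at day 60: 25 × 88 + 25 × 196 = 7100 days; shortfall 1 − 6400/7100 = 9.9%.

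**Effect of an onset-date rule.** Take 25 of 50 subjects with events at day 45 (151.6). If one of those onsets is fully missing, the rate is 152.7 if it is set to day 1 and 147.9 if set to day 196. The rule has to be stated, but it moves the result far less than the choice between 93 and 152.

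**The case against.** The strongest reply is grammatical. In the SAP sentence the initial-occurrence qualifier attaches to the subjects, while the time is labelled as time at risk for TEAEs. The formula returns the TEAE window, since last dose + 29 minus first dose counts through last dose + 28. On that reading sentence and formula agree, and subjects with the event per total follow-up time is a recognised exposure-adjusted rate.

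This reading is possible, and it limits the point. A reader might infer a proven contradiction, but the text supports only an inconsistency with two readings. It does not remove the point. At first dose essentially every treated subject is still at risk of a first treatment-emergent event, so the qualifier would exclude almost nobody. The SAP does not say that this is what it means.

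A reader might also take 35% as a minimum for the ALIS row of subjects with at least one TEAE, from the Protocol 9.9.6 statement. The documents do not support that. The figure needs a full 196-day window for every subject and the carry-over of a finding from a refractory population. Protocol 4.2.1 keeps subjects who stop ALIS/ELC on the oral drugs, which limits the shortening of windows. Rescue therapy, however, ends all randomized treatment (Protocol 5.2.2), and subjects may leave the study (Protocol 4.2.2). The Protocol 9.9.6 statement also concerns the first AE of any kind, so it says nothing about individual preferred terms.

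The low stakes are conceded as well. SAP 7.2 disclaims inference, and no between-arm EAR ratio or test is planned, so the documents do not support a claim that a planned treatment comparison is biased.

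**Conclusion.** The wording and the formula in SAP 12.4 need to be reconciled. If a first-event rate is intended, the formula understates it in each arm by p × (1 − t/T) when all windows are full. That is about 38.5% for an event with 50% incidence and onset at day 45, 15% at 20% incidence and under 5% at 5% incidence. These sizes rest on assumed incidences and onset days. The 35% for 50% incidence and onset at day 60 is illustrative; it falls to about 10% if every subject with the event stops all drugs that day.

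If a total-follow-up rate is intended, the numbers stand and only the wording is wrong. The crude n (%) columns and the primary objective are unaffected either way. The change should be made because the EAR goes into the TEAE tables and either repair is cheap.

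**What to change.** Choose one.

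**(a) Make the formula a first-event rate.** For each event category, set time at risk = min(date of first onset of that event, last dose + 28, subject's own EOS date) − first dose date + 1. In addition:

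- State that the +1 puts all branches on one inclusive day count. The last-dose branch is unchanged, and the EOS branch gains one day (196 instead of 195 when EOS is 28 days after last dose).
- State which last dose applies: the drug stopped last, which matches the TEAE window, or the specific drug for drug-specific rows. Disclose this as a clarification of the present note on study drug.
- Specify the subject's own EOS date, because Protocol 3.5 defines EOS by the last subject's last visit even though EOS is used per subject elsewhere (for example SAP 12.1).
- Add an onset rule for TEAEs with incomplete start dates, for this derivation only, and note the exception in SAP 7.4.4. One example is the earliest date that fits the known parts and is not before first dose.

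**(b) Keep the formula.** Delete the initial-occurrence qualifier at the end of the definition, and label the measure as subjects with the event per 100 patient-years of total TEAE follow-up time.

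Option (a) costs SAP wording, a per-event derivation and one date rule. Option (b) costs a wording and label edit. Neither needs new data.
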